#### 5.2.1.3 Definition of Dose Limiting Toxicity

DLT is defined as any of the following toxicities occurring during the first cycle of treatment (21 days) for each dose level. See Section 5.9 for rules on replacement of subjects in the DLT period.

The occurrence of any of the following toxicities during Cycle 1, **if assessed by the investigator to be possibly, probably or definitely related to MK-8628**, will be considered a DLT:

**Hematologic Toxicity:**

AML

1. Pancytopenia with a hypocellular bone marrow and no marrow blasts lasting for  $\geq 6$  weeks after the start of a cycle. For subjects with AML who have a suspected DLT in case of pancytopenia with a hypocellular bone marrow and no marrow blast on Day 22 bone marrow aspiration, the DLT window will be extended to the first 2 cycles or Day 42 for repeat bone marrow confirmation. However, enrollment of additional patients at this dose level should not be delayed during the extended window for DLT in this situation assuming a confirmed DLT for such a subject would not affect a dose escalation or de-escalation decision.

DLBCL

1. Grade 4 hematologic toxicity lasting  $\geq 7$  days, except thrombocytopenia  
Grade 4 thrombocytopenia of any duration  
Grade 3 thrombocytopenia is a DLT if associated with bleeding
2. Febrile or infection related neutropenia, Grade 3 or Grade 4

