**Other Toxicity:**

1. Any drug-related AE which caused subject to discontinue treatment during Cycle 1
2. Any study drug-related toxicity resulting in a subject missing  $\geq 20\%$  of planned doses during Cycle 1.
3. Any treatment-related toxicity which causes a greater than 2 week delay in initiation of Cycle 2.
4. Grade 5 toxicity

DLTs must be reported within 24 hours to the Sponsor as Events of Clinical Interest (see Section 7.2.3.2). If the event also meets the criteria for seriousness, follow the reporting guidelines for Serious Adverse Events (SAEs) outlined in Section 7.2.3.1.

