## 8.5 Analysis Populations

### 8.5.1 Safety Analysis Populations

**DLT Evaluable population:** subjects who receive at least 85% of the planned dose of study drug (18 days) or experience DLT during the first 21-day cycle.

The **All Subjects as Treated (ASaT)** population, also known as **treated population**, consisting of subjects who receive at least one dose of study drug, will be used for the analysis of all other safety data in this study.

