## 12.4 Response Assessment of AML

Table 13 Response Assessment of AML [45]

Category	Definition
Complete remission (CR)*	Bone marrow blasts < 5%; absence of blasts with Auer rods; absence of extramedullary disease; absolute neutrophil count $> 1.0 \times 10^9/L$ (1000/ $\mu$ L); platelet count $> 100 \times 10^9/L$ (100 000/ $\mu$ L); independence of red cell transfusions
CR with incomplete recovery (CRI)†	All CR criteria except for residual neutropenia ( $< 1.0 \times 10^9/L$ [1000/ $\mu$ L]) or thrombocytopenia ( $< 100 \times 10^9/L$ [100 000/ $\mu$ L])
Morphologic leukemia-free state‡	Bone marrow blasts < 5%; absence of blasts with Auer rods; absence of extramedullary disease; no hematologic recovery required
Partial remission (PR)	Relevant in the setting of phase 1 and 2 clinical trials only; all hematologic criteria of CR; decrease of bone marrow blast percentage to 5% to 25%; and decrease of pretreatment bone marrow blast percentage by at least 50%
Cytogenetic CR (CRC)§	Reversion to a normal karyotype at the time of morphologic CR (or CRI) in cases with an abnormal karyotype at the time of diagnosis; based on the evaluation of 20 metaphase cells from bone marrow
Molecular CR (CRM)¶	No standard definition; depends on molecular target
Treatment failure	
Resistant disease (RD)	Failure to achieve CR or CRI (general practice; phase 2/3 trials), or failure to achieve CR, CRI, or PR (phase 1 trials); only includes patients surviving $\geq 7$ days following completion of initial treatment, with evidence of persistent leukemia by blood and/or bone marrow examination
Death in aplasia	Deaths occurring $\geq 7$ days following completion of initial treatment while cytopenic; with an aplastic or hypoplastic bone marrow obtained within 7 days of death, without evidence of persistent leukemia
Death from indeterminate cause	Deaths occurring before completion of therapy, or $< 7$ days following its completion; or deaths occurring $\geq 7$ days following completion of initial therapy with no blasts in the blood, but no bone marrow examination available
Relapse¶	Bone marrow blasts $\geq 5\%$ ; or reappearance of blasts in the blood; or development of extramedullary disease

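### The AML DLT window runs to Day 42 for suspected marrow aplasia but stops at Day 21 in the DLT lead-in and the SAP, so some aplasia cases have no settled score

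*Combined protocol and SAP*

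**What the plan says.** **Protocol 5.2.1.3, general rule.** "DLT is defined as any of the following toxicities occurring during the first cycle of treatment (21 days) for each dose level". A second sentence, placed over the whole list, repeats the limit: "The occurrence of any of the following toxicities during Cycle 1", if the investigator judges the toxicity at least possibly related to MK-8628.

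**Protocol 5.2.1.3, AML.** There is one hematologic item: "Pancytopenia with a hypocellular bone marrow and no marrow blasts lasting for" at least 6 weeks from the start of a cycle. If the Day 22 marrow raises the suspicion, "the DLT window will be extended to the first 2 cycles or Day 42 for repeat bone marrow confirmation". Enrollment at that dose need not wait, provided that a confirmed DLT in that subject would not change the escalation decision.

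**Protocol 5.2.1.3, other toxicity.** Item 3 is "Any treatment-related toxicity which causes a greater than 2 week delay in initiation of Cycle 2". Item 4 is "Grade 5 toxicity", with no window of its own. Items 1 and 2 cover drug-related discontinuation in Cycle 1 and toxicity that causes at least 20% of planned Cycle 1 doses to be missed.

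**SAP.** Sections 8.1 and 8.4.1 define the primary endpoint as the proportion of subjects with at least one DLT in Cycle 1, Days 1 to 21. Section 8.5.1 defines the DLT-evaluable population as "subjects who receive at least 85% of the planned dose of study drug (18 days) or experience DLT during the first 21-day cycle". None of the three mentions the AML extension.

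**The concern.** The extension acknowledges that aplasia arising in Cycle 1 cannot be confirmed until about Day 42. Nothing else in the DLT machinery was moved to match, which leaves two cases open.

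- A subject with suspected aplasia on Day 22 dies of a drug-related cause before the repeat marrow. The duration item cannot be completed, and on the literal lead-in the death is too late for the Grade 5 item.
- A subject survives and has the aplasia confirmed at Day 42. That is a DLT under 5.2.1.3 but lies outside the SAP's Days 1 to 21.

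The protocol foresees deaths of this kind. Table 13 in Section 12.4 has a category that begins "Deaths occurring $\geq 7$ days following completion of initial treatment while cytopenic". That is an efficacy category and settles nothing about DLT scoring, but it shows the event is not far-fetched. At stake is the AML DLT count, which feeds Table 4, the RP2D threshold (DLT rate below 25%) and the credible interval in Section 8.6.1.

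**Working it through.** **1. Day arithmetic.** Cycle 2 is due on Day 22 (Section 5.2.2). A delay of more than 14 days is reached only after Day 22 + 14 = Day 36. Six weeks is 42 days. Cycle 1 has 21 × 2 = 42 doses.

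**2. One subject against the literal text.** Take an AML subject with at least 85% of Cycle 1 dosing, suspected aplasia on the Day 22 marrow, and drug-related death on Day 30.

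| Item | Met? | Why |
|---|---|---|
| Aplasia for at least 6 weeks, repeat marrow | No | Day 30 is before Day 42; no repeat marrow |
| Grade 5 | No | Lead-in limits it to Cycle 1 |
| Cycle 2 delay over 2 weeks | No | 30 − 22 = 8 days |
| At least 20% of Cycle 1 doses missed | No | Needs 42 × 0.20 = 8.4, so 9 doses; at 85% dosing at most 42 × 0.15 = 6.3, so 6, were missed |
| Discontinued in Cycle 1 for a drug-related AE | No | Dosing was not stopped in Cycle 1 |
| Evaluable under 8.5.1 | Yes | 21 × 0.85 = 17.85, so 18 days, was reached |

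The subject stays in the denominator with no DLT. Section 5.9 would not replace the subject.

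**3. The wider reading.** If the extension moves the whole DLT window to Day 42 for this subject, the Grade 5 item applies on Day 30 and the subject is a DLT. The same text therefore supports 0 or 1.

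**4. Reproducing the plan's figures.** An mTPI calculation with a Beta(1,1) prior, target 0.25 and DU when P(rate > 0.25) > 0.95 matches all 63 Table 4 cells for 0 to 6 toxicities. The 0.95 cutoff and the equal interval half-widths (any of 0.01 to 0.05 works) are assumptions, because the plan states neither. Table 11 reproduces to three decimals, with highest-posterior-density Bayes intervals and Clopper-Pearson confidence intervals.

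**5. Effect of one subject.** The observed rate moves by 1/6 = 16.7 points or 1/14 = 7.1 points.

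| True count | Read as | Table 4 decision | 80% interval (Table 11), true → read |
|---|---|---|---|
| 1/6 | 0/6 | S → E | (0.040, 0.391) → (0, 0.205) |
| 3/6 | 2/6 | D → S | (0.279, 0.721) → (0.146, 0.567) |
| 2/7 | 1/7 | S → E | not tabulated |

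Across the 54 cells with 0 to 5 toxicities and n = 6 to 14, adding one DLT changes the decision in 21.

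**6. Illustration only.** Start from Binomial(6, p), add one subject at each S cell, and stop at any other cell or at n = 14. P(Escalate) is then the mass absorbed in E cells. The share of DLTs lost on this path is not in the documents, so a range is shown.

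| True DLT rate | Share lost | Apparent rate | P(Escalate) |
|---|---|---|---|
| 25% | 0% | 25% | 0.487 |
| 25% | 5% | 23.75% | 0.522 |
| 25% | 10% | 22.5% | 0.559 |
| 25% | 20% | 20% | 0.634 |
| 4% | 0% | 4% | 0.991 |
| 4% | 20% | 3.2% | 0.995 |

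The 25% is the design target. The 4% is the Cycle 1 DLT rate in acute leukemia reported in Section 4.1.1.3 (3 of 75), at other doses and schedules.

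**The case against.** **The literal reading may not be the intended one.** The list contains items that can be established only after Day 21: the 6-week aplasia and the Cycle 2 delay. The lead-in may therefore mean toxicity that arises in Cycle 1. Section 7.2.4 follows grade changes within one episode, so aplasia that worsens to death could count as Grade 5. A Cycle 2 that never starts because of toxicity might also be argued under the delay item. This is a fair reading, but it is not written, and the SAP has no matching extension. Two defensible readings with opposite scores for the same subject is the problem itself.

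**Other items catch many of these subjects.** Section 5.2.1.5 requires a hold for drug-related Grade 4 hematologic toxicity, and nine missed doses or a Cycle 1 discontinuation is already a DLT. This stands and narrows the gap. It does not close it: Table 1 sets no blood-count limits for AML entry, and the first scheduled on-treatment AML marrow is at Cycle 2 Day 1. An earlier marrow is required only for Grade 4 thrombocytopenia lasting more than 3 days.

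**Loss of follow-up is easily overstated.** A reader might infer that a subject who discontinues is not assessed again until a visit 6 weeks later. The documents do not support that. Section 7.1.2.7.1 lists the Treatment Discontinuation Visit as an AML assessment, and safety follow-up continues under 7.1.5.4.1.

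**Decision-makers would see the case.** A suspected DLT is reported as an event of clinical interest, and such a death as an SAE within 24 hours. The Safety Review Committee decides on available safety and toxicity data, not on Table 4 alone. This stands for escalation, but it does not settle the DLT count, percentage or credible interval.

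**Conclusion.** The inconsistency is real and concerns the primary endpoint. For AML subjects with suspected aplasia on the Day 22 marrow, 5.2.1.3 uses a window to Day 42, while its own lead-in and Sections 8.1, 8.4.1 and 8.5.1 use Cycle 1. A drug-related death on Days 22 to 36 in a subject with at least 85% dosing is DLT-free on the literal text and a DLT on the wider reading. An aplasia DLT confirmed at Day 42 is a protocol DLT that the SAP endpoint does not capture.

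A reader might go further and infer that the plan scores such deaths as non-DLTs, or that the aplasia item requires survival. Neither is written: the first is one reading of the lead-in, and the second is an inference from the duration and the repeat marrow. Nor do the documents show that AML escalation was biased. The committee could look beyond the count, the frequency of such cases is unknown, and an Escalate result at 30 mg BID only means staying there. The 0.487 to 0.634 shift rests entirely on assumed rates. At a 4% DLT rate the same 20% loss is almost invisible (0.991 to 0.995).

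What can be stated without assumption is that one subject can change the Table 4 cell and moves the AML rate by 7.1 to 16.7 points. Section 1.0 closes enrollment, so what remains is how the rate is analysed and reported.

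**What to change.** Reconcile Sections 5.2.1.3, 8.1, 8.4.1 and 8.5.1:

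- Make the SAP endpoint and the DLT-evaluable definition use the extended window of 5.2.1.3 for AML subjects with suspected aplasia on the Day 22 marrow.
- State whether the other DLT items, including Grade 5, apply through that window for those subjects.
- Do not let an unresolved suspected aplasia DLT default to DLT-free. Report the AML DLT rate and 80% credible interval twice, with such subjects counted as DLTs and as non-DLTs.

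Excluding or replacing these subjects is not a good alternative. Section 5.9 replaces only DLT-free subjects below 85% of dose, and dropping subjects because their suspected toxicity was never resolved is an informative exclusion that could still understate the rate.

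The cost is a short text change and one sensitivity row in the DLT table. The reported AML DLT rate may be slightly higher. No further subjects or assessments are needed.

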**Non-Hematologic Toxicity:**

1. Grade 4 non-hematologic toxicity (not laboratory)
2. Grade 3 non-hematologic toxicity (not laboratory) lasting  $> 3$  days despite optimal supportive care. Grade 3 nausea, vomiting or diarrhea will be considered a DLT if lasting more than 3 days despite optimal supportive care.
3. Any Grade 3 or Grade 4 non-hematologic laboratory abnormality, if
  - medical intervention is required, or
  - the abnormality leads to hospitalization, or
  - the abnormality persists for  $> 1$  week
4. Any of the following liver test abnormalities\*\* are observed (see also Section 12.8):
  - ALT or AST  $> 8X$  ULN
  - ALT or AST  $> 5X$  ULN for more than 2 weeks
  - ALT or AST  $> 3X$  ULN **AND** (total bilirubin  $> 2X$  ULN **OR** INR  $> 1.5$ )
  - ALT or AST  $> 3X$  ULN with the appearance of fatigue, nausea, vomiting, right upper quadrant pain or tenderness, fever, rash and/or eosinophilia ( $> 5\%$ ), unless the investigator assesses the rash or fatigue to be related to MK-8628 and not related to liver impairment with sponsor's agreement.

**Other Toxicity:**

1. Any drug-related AE which caused subject to discontinue treatment during Cycle 1
2. Any study drug-related toxicity resulting in a subject missing  $\geq 20\%$  of planned doses during Cycle 1.
3. Any treatment-related toxicity which causes a greater than 2 week delay in initiation of Cycle 2.
4. Grade 5 toxicity

DLTs must be reported within 24 hours to the Sponsor as Events of Clinical Interest (see Section 7.2.3.2). If the event also meets the criteria for seriousness, follow the reporting guidelines for Serious Adverse Events (SAEs) outlined in Section 7.2.3.1.

**5.2.1.4 Recommended Phase 2 Dose (RP2D)**

Selecting the RP2D will involve a multi-faceted decision taking into account safety, tolerability, early efficacy signal, PK exposure and PD markers. The primary endpoint driving dose selection is the DLT rate, with weight given to the highest DL tolerated (< 25% DLT rate). All other facets will be considered supportive. It is important to note that dose selection in this study aims to assess a recommended phase 2 dose range, with other factors aside from those mentioned above, such as target engagement, contributing to refining the dose selection for phase 2. This will be further evaluated in subsequent clinical investigations in either monotherapy or combination trials.

**5.2.1.5 Dose Adaptation**

The Common Terminology Criteria for Adverse Events version 4.0 (CTCAE 4.0) must be used to grade the severity of adverse events. For AEs not specifically addressed in Section 5.6, MK-8628 will be withheld for drug related Grade 4 hematologic toxicities, non-hematological toxicity  $\geq$  Grade 3 including laboratory abnormalities, and severe or life-threatening AEs as per [Table 5](#) below. If a dose of MK-8628 is withheld for toxicity, then subjects may resume dosing with MK-8628 if that is appropriate at their next scheduled appointment or when toxicity has improved as described below or in Section 5.6.

Table 5 Dose Modification Guidelines for Drug-Related Adverse Events

Toxicity	Grade	Hold Treatment (Y/N)	Timing for restarting treatment	Dose/Schedule for restarting treatment	Criteria for discontinuation after consultation with Sponsor
Hematologic toxicity  DLBCL	1, 2, 3	No	N/A	N/A	N/A
	3 associated neutropenia with infection; or Thrombocytopenia with bleeding or lasting > 7 days	Yes	Toxicity resolves to Grade 0-1, or to baseline	Resume treatment at next lowest dose level ( Table 6 )	Toxicity does not resolve within 2 weeks of last dose. Permanent discontinuation should be considered for any severe or life-threatening event
	4 or Febrile neutropenia	Yes	Toxicity resolves to Grade 0-1, or to baseline	Resume treatment at next lowest dose level ( Table 6 )	Toxicity does not resolve within 2 weeks of last dose. Permanent discontinuation should be considered for any severe or life-threatening event
Hematologic toxicity  AML	1, 2, 3	No	N/A	N/A	N/A
	4 or Pancytopenia with a hypocellular bone marrow and no marrow blasts lasting $\geq$ 6 weeks after the start of a cycle.	Yes	Toxicity resolves to Grade 0-1, or to baseline	Resume treatment at next lowest dose level ( Table 6 )	Toxicity does not resolve within 2 weeks of last dose. Permanent discontinuation should be considered for any severe or life-threatening event

Toxicity	Grade	Hold Treatment (Y/N)	Timing for restarting treatment	Dose/Schedule for restarting treatment	Criteria for discontinuation after consultation with Sponsor
Non-Hematologic Laboratory Abnormalities	1, 2	No	N/A	N/A	N/A
	3, 4 with or without symptoms lasting > 48 hours	Consider holding; Hold treatment for total bilirubin increases >2X ULN or 2X baseline (if elevated at baseline) and/or AST or ALT $\geq$ 5X ULN	Toxicity resolves to Grade 0-1, or to baseline	Laboratory abnormalities resolves within 1 week: treat at same dose and schedule  Laboratory abnormalities does not resolve within 1 week: may consider resuming treatment at next lowest dose level (Table 6)	Toxicity does not resolve within 2 weeks of last dose. Permanent discontinuation should be considered for any severe or life-threatening event
Non-Hematologic toxicity  Note: Exception to be treated similar to Grade 1 toxicity	1	No	N/A	N/A	N/A
	2 Any intolerable G2 non-hematologic toxicity lasting >7 days with or without dose reduction	Consider holding for persistent symptoms	Toxicity resolves to Grade 0-1 or baseline	Clinical AE resolves within 2 weeks: treat at same dose and schedule  Clinical AE does not resolve within 2 weeks: may consider resuming treatment at next lowest dose level (Table 6)	Dose is interrupted for > 2 weeks.
	3, 4 unless not optimally treated with supportive care (e.g., Grade 3 vomiting not adequately treated according to anti-emetic standard of care)	Yes	Toxicity resolves to Grade 0-1 or baseline	Resume treatment at next lowest dose level (Table 6)	Toxicity does not resolve within 2 weeks of last dose. Permanent discontinuation should be considered for any severe or life-threatening event

After recovery from toxicity, treatment will be resumed at the next lowest dose level (Table 6). For subjects treated at DL1 (20 mg BID), treatment will be resumed at a level of 10 mg BID.

Table 6 MK-8628 Dose and Schedule Modifications

Dose Level (DL)	Initial Dose	1st Modification
DL 1	20 mg BID continuous	10 mg BID continuous
DL 2	30 mg BID continuous	20 mg BID continuous

No more than one dose reduction should be implemented unless the investigator thinks it in the subject's best interests to pursue study treatment with further dose reduction (additional dose reduction by one dose level), with the Sponsor's agreement.

Dosing interruption for > 2 weeks due to toxicity will lead to definitive study treatment discontinuation, unless the investigator thinks it in the subject's best interests to pursue study treatment, with the Sponsor's agreement.

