##### **5.6.1.1 General Guidelines for Clinically Significant Toxicities**

General guidelines regarding management and dose reduction for adverse events that are considered by the investigator to be related to study treatment are provided in Section 5.2.1.5. All adverse events should be monitored closely, with supportive care provided according to institutional standards.

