### **5.8 Subject Withdrawal/Discontinuation Criteria**

Subjects may withdraw consent at any time for any reason or be dropped from the trial at the discretion of the investigator should any untoward effect occur. In addition, a subject may be withdrawn by the investigator or the Sponsor if enrollment into the trial is inappropriate, the trial plan is violated, or for administrative and/or other safety reasons. Specific details regarding discontinuation or withdrawal procedures; including specific details regarding withdrawal from Future Biomedical Research, are provided in Section 7.1.4 – Other Procedures.

Subjects will continue study treatment until any of the following events at which point it will be definitively discontinued:

- Disease progression
- Unacceptable toxicity

- Subject withdrawal of consent
- Subject non-compliance
- Treatment interruption for > 2 weeks for any reason (except in the event of perceived benefit, with Sponsor agreement)
- Recurrence of DLT despite dose reduction (except in the event of perceived benefit, with Sponsor agreement)

However, in case of investigator's perceived benefit for the subject, treatment continuation can be considered with dose reduction despite delay/interruption > 2 weeks or reoccurrence of a DLT with the same intensity after one dose reduction. The perceived benefit of the investigator is defined by 1) any objective tumor response, or 2) any tumor regression not meeting standard response criteria, but which could improve with additional treatment, or 3) any symptomatic improvement, which, in the investigator's opinion, could not be achieved by other means. If, in the cases described above, DLT recurs with the same intensity despite one dose reduction, a second dose reduction may be considered. The decision should be discussed with the Sponsor, but the final decision must be made by the investigator. The reason for and date of dose reduction must be recorded in the eCRF and source documented in the subject's medical records.

In all cases, the reason for and date of study treatment discontinuation must be recorded in the eCRF and source documented in the subject's medical records. As far as possible, there should be only one reason for treatment discontinuation. If there are several (e.g. concomitant progressive disease and toxicity), the primary one must be reported. The subject must be followed up to establish whether the reason was an AE, and if so, this must be reported as such.

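### Section 5.2.1.5 gives two restart doses for the same recovered event, and the Table 5 cell that a site would probably follow lets some liver events meeting a DLT criterion restart at full dose

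*Combined protocol and SAP*

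**What the plan says.** Table 5 (Section 5.2.1.5) sets hold, restart and discontinuation rules by type and grade of drug-related toxicity.

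- **Laboratory row, Grade 3–4 (non-hematologic).** The restart cell reads "Laboratory abnormalities resolves within 1 week: treat at same dose and schedule". After slower recovery, a reduction is something to consider. The hold cell reads "Consider holding; Hold treatment for total bilirubin increases >2X ULN or 2X baseline (if elevated at baseline) and/or AST or ALT" at or above 5 times ULN.
- **Clinical row, intolerable Grade 2 lasting more than 7 days.** "Clinical AE resolves within 2 weeks: treat at same dose and schedule"; after slower recovery, a reduction is again optional.
- **The other four rows with a restart dose** (two DLBCL hematologic, one AML hematologic, clinical Grade 3–4) all restart one dose level down.

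The paragraph after the table reads "After recovery from toxicity, treatment will be resumed at the next lowest dose level", followed by "For subjects treated at DL1 (20 mg BID), treatment will be resumed at a level of 10 mg BID". Neither sentence is limited to particular rows.

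Liver events that count as DLTs are listed in Section 5.2.1.3, non-hematologic item 4. Table 5 has no row for them and no carve-out.

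**The concern.** A treating physician needs one answer to the question of what dose to restart. For two kinds of recovered event, Section 5.2.1.5 gives two answers. The general sentence requires a reduction; the specific cell keeps the full dose.

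The conflict matters most for the liver. If the specific cell governs, a subject whose liver tests met a DLT threshold can go back to the dose that produced them. That sits badly with two other parts of the plan. Clinical Grade 3–4 toxicity must restart lower, and Section 5.8 lists "Recurrence of DLT despite dose reduction" as a reason to stop treatment, which presupposes that a DLT has led to a reduction. Section 4.2.2 names asymptomatic bilirubin increases and Factor VII decreases among the main limiting toxicities of this drug, so liver-related laboratory findings are foreseeable.

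**Working it through.** No sample size, power or interval figure is involved. The check sets the texts side by side.

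**1. How many rows conflict.** Six Table 5 rows give a restart dose. Four allow only the next lower level. Two have a same-dose branch (laboratory Grade 3–4; clinical Grade 2). 4 + 2 = 6. The sentence after the table agrees with the four and contradicts the same-dose branch of the two.

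**2. Size of the difference (Table 6).**

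| Assigned dose | Same-dose restart | Restart one level down | Difference |
|---|---|---|---|
| DL1, 20 mg BID | 2 × 20 = 40 mg/day | 2 × 10 = 20 mg/day | 20 mg/day (20/40 = 50% lower) |
| DL2, 30 mg BID | 2 × 30 = 60 mg/day | 2 × 20 = 40 mg/day | 20 mg/day (20/60 = 33% lower) |

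**3. A liver event taken through Table 5.** Item 4 of Section 5.2.1.3 contains five triggers:

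- (a) ALT/AST above 8 times ULN
- (b) above 5 times ULN for more than 2 weeks
- (c) above 3 times with bilirubin above 2 times ULN
- (d) above 3 times with INR above 1.5
- (e) above 3 times with listed symptoms

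Trigger (a) has no minimum duration. An isolated rise of this kind meets the firm hold (at or above 5 times ULN). If it lasts beyond the row's 48 hours and then recovers to Grade 0–1 or baseline within 1 week, the laboratory cell gives the same dose. The sentence after the table gives one level down. Trigger (b) cannot use the 1-week branch if the week runs from onset; Table 5 does not say when the week starts.

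**4. Whether other text sets the restart dose.**

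- Section 5.2.1.5, lead text: begins "For AEs not specifically addressed in Section 5.6, MK-8628 will be withheld for drug related Grade 4 hematologic toxicities" and goes on to include non-hematologic toxicity of Grade 3 or more, laboratory abnormalities among them, as per Table 5. It makes restart optional, subject to being appropriate. No dose is given.
- Table 5, last column: permanent discontinuation is to be considered for severe or life-threatening events. No restart dose is given.
- Section 5.6.1.1: "General guidelines regarding management and dose reduction for adverse events" are said to be in Section 5.2.1.5, so it points back. Section 5.6.1.2 gives monitoring and points to 12.8.
- Section 12.8.3: a general recommendation to stop, only when ALT/AST is at least 3 times, bilirubin at least 2 times and ALP below 2 times ULN together. It does not reach an isolated ALT/AST above 8 times ULN.
- Sections 5.2.1.3 and 7.2.3.2: DLTs go to the Sponsor within 24 hours and suspected DLTs are treated as medically important. No dose is given.
- Table 10: advance Sponsor approval is needed to rechallenge after serious events or where re-exposure carries significant risk, by reference to the protocol's dose modification guidelines, which is the conflicting text.

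**5. The hold gap (secondary).** To escape the firm hold, ALT/AST must be below 5 times ULN and bilirubin no more than 2 times ULN, assuming normal baseline bilirubin. That rules out triggers (a), (b) and (c). Triggers (d) and (e), 2 of the 5, remain possible while ALT/AST is above 3 and below 5 times ULN. Symptoms of Grade 3 or more would bring a hold under the clinical row, so (e) counts only with milder symptoms. When bilirubin is exactly 2 times ULN and ALP below 2 times, 12.8.3 applies; below that it does not. Section 5.2.2 delays only the next cycle.

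**6. Effect on the trial's results.** Section 5.2.1.3 decides what counts as a DLT, and Table 4 turns counts into decisions. Neither uses the restart dose. The liver events above already meet a DLT criterion if they occur in Cycle 1. Change in DLT count: 0.

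**The case against.** The strongest reply is that the sentence after the table only explains what the next lower level means. It stands just before Table 6, and the line after it supplies the 10 mg BID step that Table 3 lacks. Section 5.2.1.2 says reductions depend on the toxicity encountered, which fits row-specific cells. This is probably how a site would read it. However, the sentence does not say so, and on that reading the full-dose restart in step 3 follows.

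The second reply is that judgement and Sponsor involvement surround any restart. That stands: the plan permits a full-dose restart and does not order one. None of these safeguards names a dose.

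The third is that not every DLT criterion need be a mandatory-hold criterion. That is fair, and the band is narrow. Weekly liver follow-up, 24-hour DLT reporting and the investigator's discretion to withdraw a subject all apply within it. Its extent also depends partly on CTCAE cut-offs that the documents do not reproduce. Hence the gap is secondary. The INR trigger is still worth closing, because Section 12.8.2 itself treats a raised INR as a possible sign of severe liver injury.

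The fourth is reach. DLTs exist only in Cycle 1 (apart from the AML marrow extension), enrollment is closed and one subject remains. That stands and sets the severity. It also means that a remedy tied to DLT status would miss later cycles.

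**Conclusion.** The contradiction is literal: two of six Table 5 restart rows conflict with the unqualified sentence after the table, by 20 mg/day at either dose level. If the specific cell governs, a liver event meeting a DLT criterion may restart at full dose, with isolated ALT/AST above 8 times ULN as the clear case. Secondarily, ALT/AST above 3 and below 5 times ULN, with bilirubin no more than 2 times ULN and either INR above 1.5 or symptoms below Grade 3, has no mandatory hold within the cycle.

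Severity is **minor**. The consequence is limited to patient safety and consistent dosing, and Section 1.0 leaves one subject on treatment.

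A reader might infer two stronger things that the documents do not support:

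- **That a combined ALT/AST and bilirubin rise returns to full dose unchecked.** Section 12.8.3 generally stops treatment for that pattern when ALP is below 2 times ULN.
- **That the DLT rate or the RP2D is compromised.** Step 6 shows no route to either.

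Assumptions: ULN multiples are read as printed, baseline bilirubin is normal, and ALT/AST above 8 times ULN falls within the laboratory row, whose own hold cell covers 5 times ULN and above.

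**What to change.** 1. **Reword the sentence after Table 5**, for example: *Where Table 5 requires dose reduction, restart after recovery is at the next lower dose level in Table 6.* Limit the DL1 10 mg BID sentence to the same cases.
2. **Add to the Table 5 laboratory row:** drug-related liver test abnormalities that meet the item 4 thresholds of Section 5.2.1.3 (keeping its exception for rash or fatigue not linked to the liver) or the potential-DILI criteria of Section 12.8, in any cycle, are held. If restarted, they resume only after recovery to Grade 0–1 or baseline, one dose level down (10 mg BID from DL1, 20 mg BID from DL2), and with Sponsor agreement. Isolated bilirubin rises stay under the existing row, and permanent discontinuation stays a judgement made with the Sponsor. Keying the rule to thresholds rather than DLT status makes it work after Cycle 1.

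The cost is a short wording change in Section 5.2.1.5, cross-references from 5.6.1.2 and 12.8.3 if wanted, and a letter to the site treating the remaining subject. The downside is that a subject may occasionally be held or reduced who could have continued at full dose.
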